2. OBJECTIVES AND ENDPOINTS

Primary Objectives (Safety)	Primary Endpoints (Safety)

 To assess the effect of a single course of otelixizumab treatment on the acute and long term safety and tolerability of otelixizumab in NOT1DM patients. 	
 Incidence of adverse events (AEs) particularly those related to Cytokine release syndrome (CRS). Epstein-Barr virus (EBV) reactivation over Day 21 to Month 24. Changes in laboratory values, electrocardiograms (ECGs) and vital signs over Day 14 to Month 24.
Secondary Objectives (Pharmacokinetic)	Secondary Endpoints (Pharmacokinetic)

 To assess the pharmacokinetics of repeat dose administration of otelixizumab over 14 days in NOT1DM patients. 	
 Free serum otelixizumab concentrations over Days 1-14 and summary PK parameters.
Secondary Objectives (Efficacy)	Secondary Endpoints (Efficacy)

 To assess the effect of a single course of otelixizumab treatment on the rate of decline of pancreatic β-cell function over 24 months in NOT1DM patients. 	
 Change from baseline in C-peptide and glucose AUC (0-120) after a Mixed Meal Tolerance Test at Month 3, 6, 12, 18 and 24.

 To assess the effect of a single course of otelixizumab treatment on the rate of decline of C-peptide response and insulin sensitivity of β-cell function determined after a hyperglycemic clamp over 24 months in NOT1DM patients. 	
 Change from baseline in C-Peptide and glucose AUC hyperglycemic phase [H60 to H140 minutes] and insulin sensitivity (IS) index after a hyperglycemic clamp at Months 6 and 24.

 To assess the effect of a single course of otelixizumab treatment on exogenous insulin use for otelixizumab over 24 months in NOT1DM patients. 	
 Change from baseline in mean daily insulin use over 7 consecutive days during the week preceding all visits and phone calls.

 To assess the effect of a single course of otelixizumab treatment on glycaemic control over 24 months in NOT1DM patients. 	
 Change from baseline in HbA1c level. Body weight Day -1, Months 12-24. Hypoglycemic and hyperglycemic events over Months 1-24.

Secondary Objectives (Pharmacodynamic)	Secondary Endpoints (Pharmacodynamic)

 To assess the effect of a single course of otelixizumab treatment on the time course and magnitude of CD4 + and CD8+ cells and CD3 binding and saturation on all these cells during repeat dose administration of otelixizumab over 14 days in NOT1DM patients. 	
 Relative change from baseline (%) in CD4+ and CD8+ cells, free CD3 and bound otelixizumab on CD4+ and CD8+ cells on Days 1 through 14.

 To assess the effect of a single course of otelixizumab treatment on the immunogenicity of otelixizumab in NOT1DM patients. 	
 Change from baseline in anti-drug antibody levels at Months 3 and 6.
Exploratory Objectives*	Exploratory Endpoints*

 To assess the effect of a single course of otelixizumab treatment on circulating lymphocyte populations over 24 months in NOT1DM patients. 	
 Change from baseline in absolute lymphocyte counts and ratios in some or all, but not limited to subsets (CD3+ CD4+, CD3+ CD8+, and CD19+ cells) and phenotype (eg effector, memory, regulatory T cells, eg CD45RA, CCR7+) over Week 6 to Month 24.

 To assess the effect of a single course of otelixizumab treatment on circulating lymphocytes such as regulatory T cell numbers (as quantified by CD3 and demethylated FoxP3 expression) and Th17 cells over 24 months in NOT1DM patients. 	
 Change from baseline in cell-type specific methylation marker expression in some or all, but not limited to CD3, FoxP3 and Th17 in whole blood over Week 6 to Month 24.

 To assess the effect of a single course of otelixizumab treatment on absolute numbers and ratios of circulating antigen specific CD8+ T cells over 24 months in HLA-A2⁺ NOT1DM patients. 	
 Change from baseline in absolute numbers and ratios of HLA-A2-restricted CD8 T lymphocytes reactive to specific auto-antigens (by multimer) over Week 6 to Month 24.

 To assess the effect of a single course of otelixizumab treatment on frequency of cytokine-producing antigen specific T cells over 24 months in NOT1DM patients. 	
 Change from baseline in frequency of cytokine producing cells following in vitro stimulation with auto-antigens and viral antigens (by ELISPOT) over Week 6 to Month 24.

 To assess the effect of a single course of otelixizumab treatment on serum auto-antibodies titers and serum analytes associated with treatment or autoimmune pathology over 24 months in NOT1DM patients. 	
 Change from baseline in auto-antibody titres (using a panel of common auto-antibodies associated with T1DM antigens and possibly other auto-antigens) and serum analytes (such as cytokines/chemokines) during the first 14 days of treatment and over Week 6 to Month 24.

Exploratory Objectives*	Exploratory Endpoints*

 To assess the effect of a single course of otelexizumab treatment on clonal repertoire of circulating T cell populations and/or transcriptomic gene expression changes over 24 months in NOT1DM patients. 	
 Change from baseline in T cell clonal repertoire by TCR deep sequencing over Day 6 to Month 24. Change from baseline in transcriptomic gene expression profile(s) by micro-array and/or alternative equivalent technologies including RNA sequencing at selected timepoint(s) post dosing.

 To assess the effect of a single course of otelexizumab treatment on β-cell death over 24 months in NOT1DM patients. 	
 Change from baseline in serum by measuring relative levels of unmethylated INS DNA and/or other biomarkers for β-cell death in serum over Week 6 to Month 24.

 To assess the effect of a single course of otelexizumab treatment on suppression activity of circulating T lymphocytes over 24 months in NOT1DM patients. 	
 Change from baseline in relative levels of T lymphocyte suppression using micro suppression assay over Week 6 to Month 24. Suppression activity may be further evaluated by adapting assay conditions possibly through adding and/or blocking of stimuli.

Follow up Objectives
	
Follow up Endpoints - Data from month 36 (if available) or final follow-up. This will only be applicable for patients past month 24

 To assess long term safety follow-up with otelexizumab treatment. 	
 Significant adverse events. Severe (as per ADA classification, Appendix 7) hypoglycemic events which occurred following Month 24 visit (if available) until final follow-up. Severe hyperglycemic events which occurred following Month 24 visit (if available) until final follow up. Mean daily insulin use over 7 consecutive days preceding the call. HbA1c results around time of the phone call.

*Samples will be collected and only analysed after review of safety endpoints
	

3. STUDY DESIGN

3.1. Study Design Detail

The study is a multi-centre, single-blind (see Section 5.4), randomised, placebo-controlled 6 day repeat dose study to investigate the safety, tolerability, pharmacokinetics, pharmacodynamics, efficacy and immunological profile of intravenously administered oteixizumab in New Onset Type 1 Diabetes Mellitus patients.

Approximately 40 patients will be dosed, in a dose escalation design exploring 4 dose cohorts (4 dose levels and placebo). At each dose cohort 8 patients will be randomised to oteixizumab and 2 patients to placebo.

Screening Period: Patients will be dosed within approximately 28 days of diagnosis (not more than 32 days). Insulin usage will be documented for approximately 7 days prior to Day -1. There will be a 7 - 21-day period from screening to admission to the clinic on Day -2 for the first overnight stay of the in-patient period, this time period will ensure appropriate time to review laboratory results prior to randomisation. During the screening period, total lymphocytes will be quantified on two occasions at least 3 days apart (one of the assessments may be performed on Day -1); lymphocytes must be confirmed as being within normal limits before administration of the first dose. All screening procedures are outlined in the Time and Events Table in Section 6.2.

Pre-Treatment Period: On Day -1 safety assessments will be performed as outlined in the Time and Events Table in Section 6.2. If the investigator is satisfied that the patient still meets the entry criteria they will be randomized to treatment and the hyperglycemic clamp procedure performed.

Treatment Period: Dosing will start on Day 1 and patients will remain in the unit as an in-patient for Days 1, 2 and 3 for intravenous dosing of study treatment.

Patients will be given the following flexible options for dosing on Days 4, 5 and 6:

- Option 1: Receive study treatment on an out-patient basis on any of Days 4, 5 or 6, if the Investigator is satisfied with the clinical condition of the patient. For these patients, safety monitoring will continue up to a minimum of 3 hours post-dose.
- Option 2: Patients will remain in the unit if there are any concerns about their clinical status, or if the patient prefers to remain in the unit for logistical reasons. Patients will be fully discharged from the hospital unit on Day 6 after completion of dosing and all study procedures. If the investigator considers additional safety monitoring is necessary, the patient will be asked to stay in the unit after Day 6 until they are in a satisfactory condition to be discharged.

CRS experienced from dosing to the resolution of symptoms and EBV clinical reactivation will be monitored in all the patients dosed and specific decision criteria will be used for dose escalation based on these assessments.

Within each cohort administration of study treatment for the first three patients will be staggered by at least three days across each centre.

Patients will continue to receive their usual standard of care including insulin while participating in the study.

Figure 3 shows a schematic of the overall study design.

Figure 4 shows a schematic of the study screening, dosing and follow up phases for all study patients.

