The QTc is the QT interval corrected for heart rate according to either Bazett's formula (QTcB), Fridericia's formula (QTcF), or another method, machine or manual overread.

- For subject eligibility and withdrawal, QTcF will be used.
- For purposes of data analysis, QTcF will be used as primary.

The QTc should be based on single or averaged QTc values of triplicate electrocardiograms (ECGs) obtained over a brief recording period.

11. Screening total lymphocyte counts within the normal range in two separate samples taken at least three days apart (eg screening and Day -1).
12. Capable of giving written informed consent, which includes compliance with the requirements and restrictions listed in the consent form. In the case of minors (under 18 years) written informed consent must also be obtained from a parent or Legally Acceptable Representative (LAR).

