5.4. Blinding

This will be a single blind study where the patients will not be aware of the treatment they receive. All staff including site personnel, CRO and sponsor team members will be unblinded. However, the randomisation code will be restricted to the pharmacist preparing the infusions.

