***: Stop test + REPEAT Clamp 1 day later**

Take blood samples for C-Peptide (Trasylol-EDTA on ice) and glycaemia (NaF) at:

Time	Sample Name
Time 0 + 150 min	L150
Time 0 + 165 min	L165
Time 0 + 180 min**	L180

B. Let blood glucose increase till 180mg/dL

AIM: increase BG till 180mg/dL in a period of 30 minutes.

At Time 0 + 180 min**: **STOP Actrapid IV** and **START glucose 10%** at 50 mL/hr during 15 minutes.

Measure blood glucose every 15 minutes and adapt according to [Table B](#). Blood glucose should increase to minimally 180 mg/dL with help of glucose infusion.

Table B:

	Blood Glucose (BG)	Actrapid HM Pump IV	Glucose Infusion
Adaptation of glucose infusion till BG 180mg/dl:			
15'	<180 mg/dL	STOP	Increase Glucose 10% to 100ml/h
15'	<180 mg/dL	STOP	Replace Glucose 10% by Glucose 20% at 100ml/h (same rate)
15'	<180 mg/dL	STOP	Keep Glucose 20% infusion at 100ml/h (same rate)
180-240mg/dL: START Test =Time 0***			

C. Hyperglycemic Phase start BG 180-240mg/dL

AIM: keep hyperglycaemia (range 180-240mg/dL) during 140 minutes.

When blood glucose >180 mg/dL = Time 0***

Take blood samples for C-Peptide (Trasylol-EDTA on ice) and glycemia (NaF) at:

Time	Sample Name
Time 0***	H0
Time 0 + 60 min	H60
Time 0 + 90 min	H90
Time 0 + 120 min	H120
Time 0 + 140 min	H140

Measure BG at least every 15 min and adapt according to [Table C](#).

Table C:

	Blood Glucose (BG)	Actrapid HM Pump IV	Infusion
	180-240mg/dL	STOP	Keep glucose infusion
Adaptation of glucose infusion if BG >240mg/dl:			
15'	>240 mg/dL	STOP	Glucose 10% 100ml/h
15'	>240 mg/dL	STOP	Glucose 10% 50ml/h
15'	>240 mg/dL	STOP	NaCl 0.9% 50ml/h
Adaptation of glucose infusion if BG <200mg/dl:			
15'	<200 mg/dL	STOP	Glucose 10% 50ml/h
15'	<200 mg/dL	STOP	Glucose 10% 100ml/h
15'	<200 mg/dL	STOP	Glucose 20% 100ml/h

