2.3. Study Design

Note: the study design shown is the original study design. Stopping criteria for escalation was met in Cohort 3. In addition, the duration of the study has been shortened to 24 months.

Overview of Key Study Design Features

Design Features
	
 Multi-centre, single-blind, randomised, placebo-controlled 6 day repeat dose study to investigate the safety, tolerability, pharmacokinetics, pharmacodynamics, efficacy & immunological profile of intravenously administered otelixizumab in New Onset Type 1 Diabetes Mellitus (NOT1DM) patients.

Dosing
	
 Patients dosed within ~ 28 days of diagnosis (not more than 32 days). Insulin usage documented for ~ 7 days prior to screening & Day -1 (baseline). There will be a 7-21 day period from screening to admission to the clinic on Day -2 for the first overnight stay of the in-patient period. Patients randomised on Day -1 followed by a hyperglycaemic clamp test. Dosing will start on Day 1 & patients will remain in unit for IV dosing. Patients will be given the following flexible options for dosing on Days 4, 5 and 6: Option 1: Receive study treatment on an out-patient basis on any of Days 4, 5 or 6, if the Investigator is satisfied with the clinical condition of the patient. Option 2: Patients will remain in the unit if there are any concerns about their clinical status, or if the patient prefers to remain in the unit for logistical reasons. NOTE: Within each cohort administration of study treatment will be staggered by at least three days for the first three patients across each centre.

Treatment Assignment
	
 Approximately 32 patients will be dosed in a dose escalation design exploring 4 dose cohorts (4 dose levels (9, 18, 27,36) and placebo). At each dose cohort 8 patients will be randomised to otelixizumab and 2 patients to placebo.

Interim Analysis
	
 The planned protocol defined unblinded interim analyses were:

	
 ○ Ongoing data reviews throughout the trial progression. ○ Data reviews to assess whether to dose escalate to the next cohort. ○ 12 months formal interim analysis.
--	---

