5.2. Baseline Definitions

For all endpoints (except as noted in baseline definitions) the baseline value will be the latest pre-dose assessment with a non-missing value, including those from unscheduled visits. If time is not collected, Day 1 assessments are assumed to be taken prior to first dose and used as baseline.

Unless otherwise stated, if baseline data is missing no derivation will be performed and baseline will be set to missing.

As triplicates are taken for the baseline ECG data, the average will be used as baseline. If one or two of the triplicate measurements are missing, the remaining measurement(s) will be used to calculate the average. For categorical variables for triplicate ECG assessments the worst case will be used. In terms of worseness this is defined as abnormal, clinically significant > abnormal, clinically insignificant > normal > unable to evaluate.

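### Day -1 randomisation precedes the baseline clamp and possibly the second eligibility lymphocyte result; it should follow both, and the rules on staff knowledge of allocation and on repeating an aborted clamp need reconciling

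*Protocol*

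**What the plan says.** **Order on Day -1.** Protocol 3.1 (Pre-Treatment Period) places safety assessments first; then, for patients whom the investigator still considers eligible, "they will be randomized to treatment and the hyperglycemic clamp procedure performed". SAP 2.3 is explicit: "Patients randomised on Day -1 followed by a hyperglycaemic clamp test".

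**Lymphocyte counts.** Inclusion criterion 11 (Protocol 4.2.1) requires two normal counts at least three days apart and gives screening and Day -1 as the example pair. Protocol 3.1 repeats that "one of the assessments may be performed on Day -1" and sets the first dose as the point by which normality must be confirmed. The footnote to the screening table (6.2.1) gives the same deadline.

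**Blinding.** Protocol 5.4: "All staff including site personnel, CRO and sponsor team members will be unblinded". The next sentence limits the randomisation code to the pharmacist who prepares the infusions.

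**Aborted clamp.** Appendix 6 stops the test if glucose falls below 50 mg/dL and instructs: "Stop test + REPEAT Clamp 1 day later". The schedule (6.2.2) shows the baseline clamp on Day -1 only, dosing starts on Day 1, and the visit windows in 6.1 begin at Day 14.

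**The concern.** Randomisation normally comes last, once eligibility is final and the baseline has been measured. Here it precedes one baseline and may precede one eligibility result.

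The clamp is operator-run: staff adjust insulin and glucose infusions about every 15 minutes. It supplies the baseline for change in C-peptide AUC, glucose AUC and the insulin sensitivity index, and baseline is also a covariate in the MMRM (SAP 9.1.5.1). If the operators know the assignment, the baseline is no longer guaranteed to be independent of it. The same applies to the last decision before dosing if the lymphocyte result is still awaited.

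There is also a cost that does not depend on who knows what. Protocol 4.2 allows no deviation from entry criteria, so a late abnormal count leaves a patient randomised but not dosed. SAP section 4 requires at least one dose for both the Safety and the ITT (Treated) sets, so that patient leaves both, and Protocol 5.2 forbids reuse of the randomisation number.

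**Working it through.** The plan states no figure on this point, so the check is one of sequence, clock time and the precision lost with one baseline.

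**1. Which steps can follow randomisation?**

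| Step | Timing in the documents | Relative to randomisation |
|---|---|---|
| Baseline MMTT (Protocol 6.7.1) | Screening, at least 7 days before dosing | Before |
| Day -1 safety assessments (3.1) | Day -1 | Listed before |
| Second lymphocyte result (3.1, criterion 11) | Sample may be Day -1; result due by first dose | Not fixed |
| Baseline clamp (3.1, SAP 2.3) | Day -1 | After |

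**2. Does Day -1 leave room to randomise after the clamp?** Appendix 6 aims for about 90 mg/dL at 8am on the clamp day. The phases are 180 min, a ramp with a 30 min aim, and 140 min. Allowing the ramp to take 30 to 60 min (the upper value is my assumption, from the 15-minute steps in Table B):

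- 180 + 30 + 140 = 350 min; 180 + 60 + 140 = 380 min.
- Started at 08:00, the clamp ends between 13:50 and 14:20.

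That leaves the late afternoon of Day -1 for randomisation. Protocol 5.6.1 has the infusion prepared on the day of administration, so the pharmacist does not need the assignment earlier for preparation.

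**3. Where does a repeat fall?** The day numbering runs -2, -1, 1, so one day after Day -1 is Day 1. A repeat started at 08:00 and completed before dosing would end at 13:50 to 14:20. A 12 h infusion begun then would end at 01:50 to 02:20 on Day 2, and the 9 h infusion of cohort 1 at 22:50 to 23:20 on Day 1. The documents do not schedule this, and they do not say whether dosing waits, the clamp overlaps the infusion, or the baseline is left missing.

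**4. What does one lost clamp baseline cost?** SAP 5.2 leaves a missing baseline missing, and SAP 9.1.4 allows no imputation. In units of the between-patient SD, take SE = sqrt(1/n_active + 1/n_placebo), with 8 active per dose.

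- 6 pooled placebo (2 in each of three cohorts): sqrt(1/8 + 1/6) = 0.540.
  - One active lost: sqrt(1/7 + 1/6) = 0.556; 0.556/0.540 = 1.030, or +3.0%.
  - One placebo lost: sqrt(1/8 + 1/5) = 0.570; 0.570/0.540 = 1.056, or +5.6%, in every dose contrast because placebo is pooled.
- 8 pooled placebo (four cohorts as planned): sqrt(1/8 + 1/8) = 0.500. One lost from either side: sqrt(1/7 + 1/8) = 0.518, or +3.5%.

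**The case against.** The other side has several good points.

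**Allocation.** A reader might infer from the first sentence of 5.4 that the clamp is run and the dose decision made with allocation known. The next sentence restricts the code to the pharmacist, and nothing says when other staff learn an assignment. The sentences conflict, so knowledge is possible but not established.

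**Scope.** A reader might take all efficacy baselines to follow randomisation. The MMTT baseline does not. The clamp also leaves limited discretion: Tables A to C of Appendix 6 prescribe the infusion changes, and SAP 11.5.4 uses laboratory rather than bedside glucose for the sensitivity index.

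**Eligibility.** Randomisation is conditional on the entry criteria still being met, and 3.1 says the screening interval allows laboratory review before randomisation. The first-dose deadline can be read as a backstop. This is fair, but the text never requires the Day -1 result to be back before randomisation. A count against a normal range also leaves little room for judgement. Protocol 4.1 provides for replacement on the same treatment, which could restore numbers, though the replacement's arm would then be fixed in advance.

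**Repeat clamp.** It would be too strong to say that no pre-dose repeat is possible. Step 3 shows it is tight and unscheduled, but neither excluded nor arithmetically impossible.

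**SAP 5.2.** The rule "If time is not collected, Day 1 assessments are assumed to be taken prior to first dose and used as baseline" might suggest that a clamp run during the infusion could pass as baseline. The documents do not support that. Clamp sampling times are planned data: the AUC in SAP 11.5.4 uses actual times, and listing shell OTHER_L8 shows the time each sample was taken.

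**Timing and weight.** The primary objective is safety, no formal hypothesis is tested, and SAP 2.3 records that stopping criteria were met in Cohort 3. The order cannot be changed for patients already randomised.

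**Conclusion.** The point holds as a cheap improvement to the stated order, not as a finding of bias. The documents establish that randomisation precedes the baseline clamp, that the second lymphocyte result is not required before randomisation, and that the repeat rule lands on the first dosing day without a scheduled slot. They leave open whether anyone but the pharmacist knew the assignment.

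The consequence is confined to the clamp endpoints and to any patient randomised but not dosed. The loss of precision is 3.0% to 5.6% per lost baseline with 6 placebo patients. That assumes full arms, equal variances and an unadjusted comparison of means; the MMRM figures will differ somewhat. No abort rate for clamps or failure rate for the second count is given, so the number of patients affected cannot be estimated from the documents.

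**What to change.** 1. In Protocol 3.1 and SAP 2.3, state that RAMOS randomisation takes place only after the second lymphocyte count is reported within normal limits and the baseline clamp has been performed, for example late on Day -1.
2. In Protocol 5.4, reconcile the two sentences: state who knows the allocation and from what time.
3. Reconcile the Appendix 6 instruction to repeat an aborted clamp one day later with the Day 1 start of dosing, since no pre-dose repeat is scheduled. How they are reconciled is for the sponsor and investigators to decide.

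The cost is wording in the two documents. The one small downside is that the pharmacist learns the assignment later.
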